4.2 Baseline Visit

The potential participant will return to the urology clinic to review pathology results and treatment options within 4 weeks of TURBT. This is a routine post-TURBT follow-up visit (i.e. baseline visit). If the potential participant is deemed eligible for both radical cystectomy and chemoradiation by the treating urologist, the potential participant will then be randomized either to radical cystectomy arm or chemoradiation arm.

Each participant will be assigned a unique subject identifier (subject ID) that has no meaning external to the study database. The participant identifiers will be further masked and password protected, and stored only on a secure server behind a "firewall". Only authorized research study members will have access to these identifiers. A research study file will be kept for each participant accrued. This file will include the participant's consent, the assigned unique subject identifier, and copies of relevant source documents. All participant records will be securely stored in the Urology research offices at the MARC. A data entry system will be prepared in RedCap for the study. Both the subject identifier, sequence number, and the treatment assignment for each patient will be entered into the database together with clinical outcome data collected across visits.

During this visit, the participant will complete a study questionnaire packet, which may include and not limited to demographics, medical history; and study questionnaires *such as* EORTC QLQ C30 and FACT-BI. In the interest of time, the study questionnaire packet may also be completed at participant's home and return to the study team via mail or email (per participant preference). Study team member will strongly encourage participant to complete the study questionnaire at

the time of baseline visit. If the participant completes the questionnaires from home, a study team member may follow-up with the participant over the phone, if the completed questionnaires are not received within a week of the visit. Two tubes (~ 10 mL or 2 teaspoons each) of research blood will also be drawn. Study team member or clinic staff will record participant's height, weight, and vital signs. At the completion of the baseline measurements, each participant will be randomized to either "Radical Cystectomy" or "Chemoradiation" following a process through sequentially numbered, opaque sealed envelopes by an authorized research study member.

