4.3. Required Evaluations/Management (baseline prior to initiation of any protocol treatment)

- a) Cystoscopic evaluation by the participating urologic surgeon no more than 6 weeks prior to registration will include bimanual examination under anesthesia, as thorough as possible, a transurethral resection of the bladder tumor. Patients referred from an outside hospital with a muscularis propria-invading bladder tumor will be re-resected by the participating urologist.
- b) Radiologic evaluation including chest CT, abdominal and pelvic CT and bone scan no more than 6 weeks prior to start of treatment.
- c) Comprehensive metabolic panel (CMP) obtained no more than 4-6 weeks prior to registration

5. Randomization

5.1 Radical Cystectomy Arm- Those randomized to “Radical Cystectomy” will be scheduled for surgery. In brief, radical cystectomy is the removal of the entire bladder, nearby lymph nodes (lymphadenectomy), part of the urethra, and nearby organs that may contain cancer cells. In men the prostate, the seminal vesicles, and part of the vas deferens are also removed. In women the cervix, the uterus, the ovaries, the fallopian tubes, and part of the vagina are also removed. Participants in this group may also undergo neoadjuvant chemotherapy prior to the surgery as is the current standard of care. The decision for specific chemotherapy regimen is based on medical oncologist’s evaluation. All AE occurring during the study period will be assessed and attribution assigned.

The surgical approach, robotic versus open, is determined by patient and surgeon mutual preference. All urinary diversions will be done via an open incision and the mode of diversion, whether intracorporeal or extracorporeal (orthotopic neobladder, continent cutaneous diversion or ileal conduit) will be selected by mutual agreement of the surgeon and patient, as is customarily done. The extent of the lymph node dissection will be determined by the surgeon but at minimum will include the external iliac, obturator, and hypogastric regions.

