Lymph node dissection: Minimum lymph node (men and women) – all potential lymph node bearing tissue with the lateral limit the genitofemoral nerve, distally Cooper’s ligament to include the lymph node of Cloquet, proximally the crossing of the ureter over the common iliac vessels, medially the bladder to include the tissue medial to the hypogastric artery, posteriorly the floor of the obturator fossa with circumferential mobilization of the external iliac artery and vein.

5.2 Chemoradiation Arm - Those randomized to chemoradiation will undergo radiation therapy concurrently with chemotherapy which serves as radiosensitizer. The following is a brief outline of the radiation therapy. Specific treatment frequency and dosage will be at the discretion of the treating physician/center.

Radiation Therapy (Protocol treatment must begin within 8 weeks following transurethral resection and endoscopic evaluation)

All patients who are randomized to bladder preservation arm will receive the induction course of chemoradiation first. This regimen will begin within 8 weeks following the TUR and cystoscopic evaluation by the participating urologic surgeon. Patients with a complete response to the induction regimen will receive consolidation chemoradiation, starting 7-14 days after cystoscopic re-evaluation. Ideally, treatment should begin on a Monday for both Induction and Consolidation chemoradiation.

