5.2.7 Treatment Interruption (12/6/15)

If a grade 3 hematologic toxicity (ANC or platelets) develops during chemoradiotherapy, all treatment (both radiation and chemotherapy) should be discontinued for a minimum of 1 week.

Treatment may be resumed when the hematologic toxicity resolves to \leq grade 2. If these laboratory values have not been reached after a 1-week delay, they should be checked weekly until they become acceptable. If after 3 weeks the blood counts have not recovered, all protocol treatment should be discontinued and the patients should be treated on an individual basis.

For a grade 3 acute colitis, cystitis, or any other grade 3 infield (radiation-related) toxicity during any treatment week, treatment should be delayed until the toxicity subsides to the grade 2 level. If the delay is greater than 3 weeks, then the patient should be considered intolerant of protocol therapy and appropriate off-protocol therapy given.

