5.3 DRUG THERAPY

Medical Oncologist will determine the chemotherapy regimen concurrently used with radiation as a radiation sensitizer. The following is a list of chemotherapeutic drugs that could be used per NCCN guideline:

Cisplatin

Cisplatin and 5-FU

5-FU and Mitomycin

Cisplatin and Paclitaxel

Low dose gemcitabine

All AE occur during the study period will be assessed and attribution assigned.

6. Post-Induction Response Evaluation (for Chemoradiation Arm only)

Following the completion of induction chemoradiotherapy and the evaluation of response all patients must be re-registered via cystoscopy and biopsy. At this time, the response results (biopsy results and cytology results) and the second phase of the treatment (i.e. radical cystectomy for tumor response $T \geq 1$ or consolidation chemoradiotherapy for tumor response T0, Ta, and Tcis) will be recorded and a new data collection calendar generated. Details regarding “Radical Cystectomy” can be found at Section 5.1. Details regarding “Consolidation Chemoradiotherapy” can be found at Section 5.2.2.

The following information will be supplied:

- original case number
- results of evaluation and pathologic T stage
- treatment start date (radical cystectomy or consolidation chemoradiotherapy)

The treatment option registered and the new data collection calendar will be based on the parameters specified by the protocol. If the investigator or the patient deviates from the protocol specified treatment, documentation of this and data submission as outlined in our study Standard operating procedure.

Patients who have developed distant metastases during the induction phase of treatment and who will not continue therapy will remain on the original calendar schedule for continued follow up only.

After completing either radical cystectomy or consolidation chemoradiotherapy, all response results to the second phase of treatment (i.e., either pathologic staging from the radical cystectomy or cystoscopic re-evaluation performed following completion of consolidation chemoradiotherapy) will be promptly submitted to Data Management.

7. 1 Post-Treatment Study Visits at 3, 6, 9, 12, 18, 24, 30, and 36 month \pm 1 month

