8.2 CHEMORADIATION ARM

	Initial Visit	Pre-Treatment (tx) TURBT	Baseline	Treatment Period: Chemoradiation	Post-Induction Response Evaluation with Cystoscopy and biopsy (3-4 weeks following Induction Chemoradiotherapy) and second phase of treatment**	Post-tx 3 mon f/u ± 1 mon	Post-tx 6 mon f/u ± 1 mon	Post-tx 9 mon f/u ± 1 mon	Post-tx 12 mon f/u ± 1 mon	Post-tx 18 mon f/u ± 1 mon	Post-tx 24 mon f/u ± 1 mon	Post-tx 30 mon f/u ± 1 mon	Post-tx 36 mon f/u ± 1 mon (end of study visit??)			
Study eligibility	X		X													
Informed consent	X															
Assessment of AE								X	X	X	X	X	X	X	X	X
SOC Image studies (X-Ray, CT, and/or MRI)			X					X	X	X	X	X	X	X	X	X
Radiation & Medical Oncology Consults (SOC)			X													
Research blood sample			X					X	X	X	X	X	X	X	X	X
Ht, Wt, and Vitals [#]			X					X	X	X	X	X	X	X	X	X
Research Study Questionnaires			X					X	X	X	X	X*	X*	X*	X*	X*

Note:

SOC = Standard of Care

information may be extracted from EMR

*Research study questionnaire may be emailed or mailed per patient's stated preference

** Post-treatment cystoscopy is SOC for chemoradiation patients ONLY

**Pending on the results of post-induction TURBT and response evaluation, participant may receive further treatments. Details on the second phase of treatment are listed in Section 6 and Study Synopsis.

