9. DATA COLLECTION & STUDY EVALUATIONS

Medical records will be reviewed prior to “Baseline Study Visit” to confirm study eligibility. After obtaining consent, socio-demographic data will be collected through chart review and interviews. Clinical data that will be collected include but not limited to bladder cancer treatment history, tumor characteristics, stage, laboratory results, medications and co-morbidity.

Study team member or clinic staff will measure height, weight, and vital signs at each specific study time point. Research blood will be drawn at each study time point. Blood and tissue samples may be banked under the optional study (HSC20050234H GU Tissue Bank). For those participants who declined to participate in the optional study, any leftover samples will be permanently de-identified through the GU Tissue Bank (HSC20050234H) honest broker system. At the close of this study, all biological materials collected will be rolled into HSC20050234 GU Tissue Bank.

9.1 Feasibility: We will report recruitment, visit dates, adherence, attrition rates and compliance with randomization for each arm of the study

9.2 Bladder-intact survival: We will report proportion of patients who failed chemoradiation and required salvage cystectomy

9.3 Quality of life: A self-assessment questionnaire using the European Organization for Research and Treatment of Cancer (EORTC) QLQ- C30 and FACT-Bladder will be used for QOL assessment at baseline, 3, 6, 9 and 12 months.⁸

9.4 Progression free survival: This will be measured from the date of finishing chemoradiation or radical cystectomy to the date of first documentation of progression. Progression will be determined using RECIST 1.1 criteria by the treating physician based on radiographic or pathologic evidence of disease progression, or death from disease. Any documented recurrence will be considered progression.⁹ The date of progression will be recorded.

9.5 Candidate gene expression analysis: For the participants who have consented to be part of the optional study (“GU Tissue Bank HSC20050234H), a microarray analysis will be performed on all bladder tumor specimens using Agilent Technologies (Agilent SurePrint G3 Human Gene Expression 8x60K v2) Microarray. Goal is to study the landscape of 50 important candidate genes, which are involved in bladder cancer (for example-BRAF, KRAS, EGFR, FGFR).

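### The PFS clock starts at the end of treatment, at an arm-specific point after randomisation, with no rule for earlier events or for patients who never finish

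*Combined protocol and SAP*

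**What the plan says.** **Time origin.** Section 9.4: "This will be measured from the date of finishing chemoradiation or radical cystectomy to the date of first documentation of progression".

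**Events.** The treating physician determines progression by RECIST 1.1, "based on radiographic or pathologic evidence of disease progression, or death from disease". Any documented recurrence also counts. No other kind of death is mentioned.

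**Randomisation.** Section 4.2: "At the completion of the baseline measurements, each participant will be randomized to either" arm. This precedes all protocol treatment.

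**From randomisation to time zero.** In the cystectomy arm, section 5.1 says: "Participants in this group may also undergo neoadjuvant chemotherapy prior to the surgery". Neither its length nor the wait for surgery is given. In the chemoradiation arm, response is evaluated "3-4 weeks following Induction Chemoradiotherapy" (section 8.2), and consolidation follows in complete responders, "starting 7-14 days after cystoscopic re-evaluation" (section 5.2).

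**Patients who do not finish.** Section 5.2.7: "If after 3 weeks the blood counts have not recovered, all protocol treatment should be discontinued". Section 6: "Patients who have developed distant metastases during the induction phase of treatment and who will not continue therapy will remain on the original calendar schedule". That rule concerns follow-up only. Section 6 also sends patients with residual tumour of T1 or higher after induction to cystectomy as their second phase.

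**Analysis.** Section 11 plans Kaplan-Meier curves by arm and a logrank test of non-inferiority. It gives no PFS analysis set, censoring rule or margin.

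**The concern.** Randomisation makes the arms comparable at the moment of randomisation. A clock that starts when treatment ends begins later, at a date that depends on the arm and, in the cystectomy arm, on whether neoadjuvant chemotherapy was given. Anything that happens to patients before that date is outside the endpoint unless a rule brings it in, and there is none.

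Two things are at stake. First, a difference between arms that arises early can be missed. Second, two competent analysts could build different PFS datasets from the same patients, because the plan does not say whether early failures and non-finishers are left out, counted at time zero or handled in some other way.

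The event definition raises a related problem. Where surgery is compared with chemoradiation, deaths caused by treatment are part of the comparison. Under section 9.4 a death enters only if it is attributed to disease, and nothing says how the others are treated. This does not break randomisation, but it makes the endpoint depend on a judgement about cause.

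**Working it through.** **1. Reading the sections together.** No section moves the PFS origin to randomisation. Three groups that the protocol itself foresees do not fit the definition:

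| Patient | What the protocol provides | What PFS lacks |
|---|---|---|
| Metastases during induction, therapy not continued (section 6) | A visit-calendar rule | A start date; the event precedes any finish |
| Protocol treatment stopped for unrecovered blood counts (section 5.2.7) | Stop rule, individual care | A stated finish date |
| Residual tumour after induction, sent to cystectomy (section 6) | Second-phase treatment | Whether time zero is the end of induction or the surgery; whether residual tumour is an event |

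**2. Length of chemoradiation.** Inputs: 20 induction and 12 consolidation fractions, once daily (section 5.2.1); evaluation 21 to 28 days after induction (section 8.2); consolidation 7 to 14 days later (section 5.2). I assume weekday fractions and no breaks, and allow any weekday start.

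- Shortest: Monday start, last induction fraction on day 25, evaluation on day 46, consolidation from day 53 (a Friday), last fraction on day 70.
- Longest: Tuesday start, last induction fraction on day 27, evaluation on day 55, consolidation from day 69 (a Monday), last fraction on day 84.

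So first to last fraction takes 70 to 84 days, or 10 to 12 weeks. The 10 weeks stated in section 5.2.1 is the lower end.

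**3. Share of patients with an event before the clock starts.** The documents give no PFS rate. As an assumption I borrow the 50% and 74% three-year disease-specific survival for stage T2 in section 1.1.1, with a constant hazard:

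p = 1 − S36^(t/36), with t in months of 30.44 days.

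| Days before the clock | S36 = 0.50 | S36 = 0.74 |
|---|---|---|
| 70 | 4.33% | 1.91% |
| 84 | 5.17% | 2.28% |

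Times 15 patients, this is 0.29 to 0.78.

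**4. Adding the wait before treatment.** Randomisation falls within 4 weeks of TURBT (section 4.2) and chemoradiation starts within 8 weeks of it (section 5.2), so the wait is at most about 56 days. With 84 + 56 = 140 days, p is 3.8% to 8.5%, or 0.6 to 1.3 of 15. For the cystectomy arm the gap is not stated. An assumed 4 to 20 weeks gives 0.8% to 8.5%, or about 0.1 to 1.3 of 15.

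**5. What this does and does not show.** These are shares of patients with an event before time zero, not biases. With constant hazards the hazard ratio after the clock starts is unchanged; bias needs an early difference. As a what-if with no source, let one arm's hazard be k times higher in the 70 to 84 days only, and equal afterwards. The drop in its 36-month event-free rate from randomisation is S36 × [1 − (1 − p)^(k−1)]:

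| k | S36 = 0.50 | S36 = 0.74 |
|---|---|---|
| 2 | 2.17 to 2.59 points | 1.41 to 1.69 points |
| 3 | 4.24 to 5.04 points | 2.79 to 3.34 points |

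If early failures are left out, PFS under section 9.4 would show a hazard ratio of 1.00 in every one of these cases, by construction.

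**The case against.** The strongest reply concerns weight and evidence, not the text.

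- **The arithmetic is soft.** The borrowed rates are disease-specific survival in T2, whereas eligibility is T2 to T4a and PFS counts any recurrence, so they do not bound PFS. The 70 to 84 days fits only patients who complete consolidation. The difference in delay between arms cannot be calculated at all, because nothing is stated for the cystectomy arm. The what-if contains its own answer. All of this stands: the figures show scale only and say nothing about bias in this trial.
- **The data are partly recoverable.** Section 9.4 records progression dates. Section 9.1 reports visit dates, attrition and compliance with randomisation by arm. Section 11 plans a CONSORT diagram. Patients with metastases during induction stay in follow-up. Deaths are serious adverse events under section 10.2, and mortality is in the quarterly report (section 10.3). This stands too, but being able to reconstruct an analysis later is not the same as specifying it beforehand.
- **Some readings are natural.** The last treatment date could serve as the finish for a patient who stops early, and section 9.4 is silent on other deaths rather than expressly excluding them. That is fair, but it confirms that a rule has to be supplied.
- **It is a pilot.** With 15 per arm and no PFS margin, the logrank test could not establish non-inferiority from any origin. That limits the severity. It does not make the definition sound.

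**Conclusion.** The concern holds. As written, section 9.4 gives an arm-specific time zero after randomisation, no rule covers events before it or patients who never reach it, and section 11 compares the arms on the result. That conclusion rests on the text alone and is firm.

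The size is modest and rests on assumptions: a constant hazard, 36-month event-free rates of 50% to 74% that are not PFS rates, and no treatment breaks. On these, fewer than one chemoradiation patient in 15 would be expected to have an event between first and last fraction, and about 1.3 at most once the longest permitted wait is added. Neither the direction nor the size of any bias can be derived from the documents.

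This should be fixed, but it is not a fatal flaw for a pilot of this size. The main consequence is for the adequately powered trial of the same design envisaged in Aim 2b, which would inherit the definition.

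**What to change.** 1. Define PFS as the time from randomisation to first progression, recurrence or death from any cause, in all randomised patients by assigned arm, with written censoring rules.
2. State how residual disease at the post-induction evaluation is classified for PFS, including in patients who go on to cystectomy.
3. Record the randomisation date, and every death with its date and cause, through month 36. Reconcile section 10.2, which ends adverse event documentation 30 days after the 12-month visit, with sections 7.1, 8.1 and 8.2, which schedule adverse event assessment to month 36.
4. Keep the section 9.4 definition as a sensitivity analysis, with a written rule for events before its origin and for patients who do not finish treatment.

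The cost is low: a revised definition and a date-of-death field to month 36. The randomisation date is largely available already, since randomisation takes place at the baseline visit. Counting all deaths will make PFS look somewhat less favourable if any such deaths occur; moving the origin alone would not, under a constant hazard with early failures left out. One limitation remains: imaging visits are timed from the end of treatment, so assessment times measured from randomisation will still differ by arm and should be reported.

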2. HYPOTHESIS AND SPECIFIC AIMS

Multiple prospective radiation therapy protocols have evaluated bladder-preserving chemoradiation therapy approach for muscle-invasive bladder cancer (MIBC), with radical cystectomy reserved for radiation failure. Aims of bladder preservation in MIBC are to offer a quality-of-life advantage and avoid potential morbidity or mortality of RC without compromising oncologic outcomes. Because of lack of level-1 evidence, oncologic equivalence of bladder preservation modality treatments compared with RC remains unknown.

2.1 HYPOTHESIS:

We hypothesized that chemoradiation is non-inferior to radical cystectomy for treatment of MIBC.

2.2 SPECIFIC AIMS:

SPECIFIC AIM 1a To determine and quantify quality of life in patients treated with radical cystectomy and chemo radiation therapy

1b To determine and quantify progression free survival and bladder-intact survival in patients treated with radical cystectomy and chemoradiation therapy,

SPECIFIC AIM 2a To evaluate genetic markers predicting response to chemoradiation by performing tissue RNA microarrays.

2b To assess the feasibility of conducting an adequately powered non-inferiority trial of the same design via recruitment rate, patient adherence to both treatment arm, and attrition.

2.3 STUDY DESIGN:

Our study will be a pilot, prospective, single-center, randomized non-inferiority trial comparing chemoradiation therapy to radical cystectomy. Patients diagnosed with muscle invasive bladder cancer after transurethral resection of bladder tumor and are surgical candidates will be randomized to either radical cystectomy (with neoadjuvant chemotherapy if suitable candidate) or chemoradiation.

Both treatment methods are considered “standard of care” recommended by the NCCN Clinical Practice Guidelines (http://www.nccn.org/professionals/physician_gls/pdf/bladder.pdf) in treating muscle invasive bladder cancer.

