Categorical outcomes will be summarized with frequencies and percentages. Continuously distributed outcomes will be summarized with the sample size, mean, standard deviation, median, minimum and maximum. A consort diagram giving the number patients screened, the number of screen failures, the number randomized, the number lost to follow-up by reason, and the number completing the study by treatment arm will be created. In Aim 1a we will test the hypothesis that chemoradiation therapy is non-inferior to radical cystectomy with regard to change in quality of life at 36 months relative to baseline. In Aim 1b, we will test the hypothesis that chemoradiation is non-inferior to radical cystectomy with regard progression free survival and bladder intact survival. With regard to Aim 1a, assuming the 50% (p_2) of patients randomized to radical cystectomy and 60% (p_1) of patients randomized to chemoradiation will experience improvement in quality of life at 3 years relative to baseline and a 5% margin (Δ) of non-inferiority, this study would require $n=171$ subjects per group to attain 80% power for testing $H_0: p_1 - p_2 \leq \Delta$ versus $H_1: p_1 - p_2 > \Delta$ with $\alpha=5\%$. The non-inferiority of chemoradiation compared with radical cystectomy with regard to changes in quality of life (Aim 1a) will be assessed with Fisher's exact test. Progression free and bladder-intact survival (Aim 1b) will be summarized by treatment arm with Kaplan-Meier curves and supporting tabulations and non-inferiority will be assessed with a logrank test. The significance of treatment arm differences with regard to biomarkers (Aim 2a) will be assessed with t-tests or Wilcoxon tests. Pairwise correlations between biomarkers will be displayed overall and by treatment arm. Logistic regression will be used to find a best linear predictor of treatment arm in terms of multiple biomarkers. Biomarkers may be log transformed prior to analysis. Feasibility (Aim 2b) will be assessed with a new power and sample size calculation. If the logistic regression model fails in Aim 2a, random forests will be attempted. If the logrank test fails in Aim 1b, Fisher's exact test will be used. R (v3+, Vienna, Austria) or SAS (SAS Institute, Cary, North Carolina) software will be used throughout.

REFERENCES

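### PFS counts only deaths from disease, so the Aim 1b comparison ignores all other deaths and would favour whichever arm has more of them

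*Combined protocol and SAP*

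**What the plan says.** Section 9.4 has the treating physician judge progression from "radiographic or pathologic evidence of disease progression, or death from disease". It adds: "Any documented recurrence will be considered progression". Time is "measured from the date of finishing chemoradiation or radical cystectomy to the date of first documentation of progression". The outline of captured data in Section 9.8 lists only RECIST 1.1 and physician assessment for PFS.

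Section 11 sets out to test that "chemoradiation is non-inferior to radical cystectomy with regard progression free survival and bladder intact survival". Both outcomes are to be "summarized by treatment arm with Kaplan-Meier curves and supporting tabulations and non-inferiority will be assessed with a logrank test". It gives no censoring rule, competing-risk method or all-cause sensitivity analysis, and for PFS no margin, hazard ratio, event count or power.

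No other endpoint fills the gap. Overall survival is not listed. Section 9.2 describes bladder-intact survival as the proportion needing salvage cystectomy after failed chemoradiation and does not mention death.

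Section 10.2 classes death as a serious adverse event but ends adverse event documentation 30 days after the 12-month post-treatment visit. The calendars in Sections 8.1 and 8.2 mark adverse event assessment through 36 months.

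**The concern.** An endpoint called progression free survival is normally read as time alive without progression. Under Section 9.4, a patient who dies without progression from an operative complication, treatment toxicity or comorbidity does not have an event. Such a death counts in no efficacy endpoint of the trial.

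This matters more than usual because the arms are major surgery and a course of chemoradiation, whose non-cancer risks may well differ. Section 2 says that bladder preservation aims to "avoid potential morbidity or mortality of RC without compromising oncologic outcomes". The endpoint can neither show a saving in operative mortality nor expose toxic deaths from chemoradiation. Whether a death counts also depends on a judgement of its cause, and no independent or blinded adjudication is described. Because the pilot is meant to inform a larger trial of the same design, the definition could carry forward.

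**Working it through.** **1. The plan's own figure.** The only sample size is 171 per group, for quality of life (Aim 1a). With rates of 50% and 60% and a 5% margin, the distance to the margin is 0.10 + 0.05 = 0.15, and the variance term is 0.5×0.5 + 0.6×0.4 = 0.49. At one-sided 2.5% and 80% power, n = 0.49 × (1.960 + 0.842)² / 0.15² = 170.9, so 171, which matches. (One-sided 5% gives 135.) This figure does not depend on the PFS definition, and there is no PFS figure to reproduce.

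**2. Effect of the event definition.** From the documents: 15 patients per arm (Sections 3.3 and 11), the event in 9.4, and the methods in Section 11. All rates below are assumptions. Let *p* be the 3-year risk of progression or disease death, and *d* the 3-year risk of other death, with independent exponential hazards.

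- PFS as defined, other deaths censored: 1 − *p*
- PFS counting all deaths: (1 − *p*)(1 − *d*)
- All-cause hazard ratio, B to A: ln(PFS in B) / ln(PFS in A)

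With *p* = 40% in both arms and *d* = 5% (A) versus 15% (B), PFS as defined is 60% in both arms, hazard ratio 1.00. Counting all deaths it is 0.60 × 0.95 = 57.0% versus 0.60 × 0.85 = 51.0%, hazard ratio 1.20. The definition overstates PFS by 3.0 points in A and 9.0 points in B.

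Over a wider assumed range, with *p* equal in both arms, the hazard ratio as defined is always 1.00, but:

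| *p* | *d*, A / B | All-cause PFS, A / B | Gap (points) | HR, B to A |
|---|---|---|---|---|
| 26% | 0% / 5% | 74.0% / 70.3% | 3.7 | 1.17 |
| 26% | 5% / 20% | 70.3% / 59.2% | 11.1 | 1.49 |
| 40% | 0% / 5% | 60.0% / 57.0% | 3.0 | 1.10 |
| 40% | 5% / 20% | 57.0% / 48.0% | 9.0 | 1.31 |
| 50% | 0% / 5% | 50.0% / 47.5% | 2.5 | 1.07 |
| 50% | 5% / 20% | 47.5% / 40.0% | 7.5 | 1.23 |

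The ranking can reverse. With *p* = 40% versus 35% and *d* = 5% versus 15%, PFS as defined is 60% versus 65% (hazard ratio 0.84, favouring B). Counting all deaths it is 57.0% versus 0.65 × 0.85 = 55.3% (hazard ratio 1.06). With 15 per arm, each uncounted death is 1/15 = 6.7% of an arm.

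**3. Effect of the time origin.** Cystectomy is finished on the day of surgery, so a postoperative death falls after time zero. Chemoradiation with both courses runs over 10 weeks (Section 5.2.1), so a patient who dies during it never reaches time zero. Nor does a cystectomy-arm patient who dies during neoadjuvant chemotherapy. If only the event were changed, operative deaths would count while deaths during chemoradiation or neoadjuvant chemotherapy would not.

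**4. Whether deaths are already collected.** Section 10.2 stops adverse event documentation shortly after month 12, while Sections 8.1 and 8.2 run to month 36. Neither vital status nor date of death is listed as a captured item, so complete dates of death to 36 months cannot be assumed.

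**The case against.** Three objections have weight.

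- **A disease-specific endpoint is legitimate.** Section 2 separates the mortality of cystectomy from oncologic outcomes, and Section 1.1.1 links the PFS aim to disease-specific survival curves. With other deaths censored, the logrank test is an accepted comparison of cause-specific hazards. This stands, provided that the endpoint is named accordingly. Section 9.4 calls it progression free survival, and no all-cause measure accompanies it.
- **Censoring is inferred.** Section 11 does not say how non-disease deaths are treated. That is correct. But Kaplan-Meier and logrank methods need every patient to be an event or censored, and 9.4 excludes these deaths as events.
- **This is a small pilot.** PFS has no margin or power, so its test could not establish non-inferiority under either definition. This lowers the severity but does not remove the defect.

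A reader might also infer that the definition favours chemoradiation, or hides surgical harm. The documents support neither: they give no non-disease death rate for either arm, and deaths are reported as serious adverse events and in the quarterly monitoring report (Section 10.3). Those reports are not a comparative endpoint, but the deaths would not go unseen.

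**Conclusion.** The point holds in this form: PFS under Section 9.4 leaves out deaths not due to disease, no other efficacy endpoint counts them, and the Aim 1b comparison would therefore favour whichever arm has more of them. The direction is unknown in advance. The size is illustrative. Under the assumed rates, with equal progression risk, the hidden gap in 3-year PFS runs from 2.5 to 11.1 points; the central example hides 6 points. This rests on other deaths being censored and on independent exponential hazards.

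A reader might infer that replacing one phrase in 9.4 is enough because deaths are already recorded. The documents do not support this: the end-of-treatment time origin and the conflicting end dates for adverse event documentation both stand in the way.

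Severity: should be fixed. A 30-patient pilot with no PFS margin or power does not warrant a higher grade.

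**What to change.** - In Section 9.4, define PFS as the time from randomization to the first of progression, recurrence or death from any cause. Use that definition in the Section 11 Kaplan-Meier and logrank analyses, and state the censoring rules there. Change the event and the time origin together.
- Record vital status and date of death for every patient through the 36-month visit, and add both to Section 9.8.
- Reconcile the end of adverse event documentation in Section 10.2 with the calendars in Sections 8.1 and 8.2.
- If a disease-only measure is wanted, report it as a secondary endpoint under its own name, with other deaths as a competing event.

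**Cost.** No added patients or visits. Date of death must be collected explicitly, and non-cancer deaths will add some events unrelated to tumour control. Starting at randomization also brings the post-induction evaluation (Section 6) inside the PFS window, so 9.4 should say whether residual tumour found there is an event.
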